10.1.2 Method of Analysis

To assess the treatment exposure, descriptive statistics (number of subjects, mean, standard deviation, median, minimum and maximum) will be presented for treatment duration (days) by treatment group and total.

Exposure data will be listed for Safety Set.

10.2 Adverse Events

10.2.1 Variable, Definition and/or Derivation

Variables	Definition and/or Derivation
Adverse event (AE)	This refers to any harmful and unintended signs (including abnormal laboratory test results, etc.), symptoms, or diseases that occur in a subject who has been administered an investigational product, and it does not necessarily must have a causal relationship to the investigational product.
Treatment-Emergent Adverse Events (TEAEs)	A TEAE is defined as an AE not present before exposure to study drug or any event already present that worsens in severity or frequency after exposure to study drug.
Adverse drug reaction (ADR)	This refers to any harmful and unintended reactions that occur at any dose of an investigational product and of which the causal relationship to the investigational product cannot be denied. TEAE will be considered to be ADR if the causality is evaluated as certain, probable/likely, possible, conditional/unclassified, or unassessable/unclassifiable.
Serious adverse event/adverse drug reaction (serious AE/ADR)	This refers to an adverse event or adverse drug reaction that occurs at any dose of an investigational product that corresponds to any one of the following: ① Occurrence of death or life-threatening risks ② Requires hospitalization or prolongation of hospitalization

Variables	Definition and/or Derivation
	
③ Results in permanent or significant disability or functional decline
 
④ Occurrence of malformations or abnormalities in a fetus
 
⑤ Other than cases ① through ④, occurrence of drug dependence or abuse, or cases in which medically significant situations occur, such as hematopathies
 
However, in this clinical study, a visit made for the following reasons will not be considered as a serious adverse event.
 
• Hospitalization planned prior to the clinical study• Hospitalization for medical examination, cosmetic reasons, and recuperation• Cases in which the time of visiting the emergency room has not exceeded 24 hours. However, it may be considered a serious adverse event based on the investigator's judgment even if it does not exceed 24 hours. 
If a situation occurs that is considered to have a significant impact on the patient's well-being and health status, even if not listed above, it shall be determined whether to consider it as a serious adverse event according to the medical judgment of the doctor in charge and relevant specialists, and appropriate measures shall be taken accordingly.

10.2.2 Method of Analysis

10.2.2.1 Overall Summary of Adverse Events

The number of subjects, incidence (%) with its two-sided 95% confidence interval and number of events will be presented for AEs, adverse drug reactions (ADRs), serious adverse events (SAEs), serious adverse drug reactions (SADRs), AEs leading to permanent discontinuation, and AEs leading to death by treatment group. The chi-square test or Fisher's exact test will be used for comparison of AE incidence between GV1001 and Placebo.

Also, Number of events for AEs/ADRs will be presented according to severity, causality to IP, and outcome.

10.2.2.2 Display of Adverse Events

All AEs and ADRs will be presented according to SOC and PT. The following conventions will be used in summarizing AEs:

- For subject incidence summaries, a subject will be counted only once within each SOC and within each PT.
- Summaries by severity – if a subject reports more than 1 AE within an SOC and/or PT, the AE with the highest severity within each SOC and within each PT will be included.

- When the number of events is calculated, more than 1 AE counted as different events

Subjects with TEAEs will be listed for Safety Set.

10.2.2.3 Death and Serious Adverse Events and Other Significant Adverse Events

For SAEs, AEs leading to permanent discontinuation, and AEs leading to death, separate listings and summaries of subject counts and percent together with the number of events will be presented by treatment group and by SOC and PT.

10.3 Clinical Laboratory Analyses

10.3.1 Variable, Definition and/or Derivation

Laboratory Tests*	Variables
Hematology test, Blood chemistry test	Change from baseline at week n = result at week n – result at baseline n=6, 14, 26
	Change from baseline at final visit result at final visit* – result at baseline *the last visit among regular visit, unscheduled visit and End visit/Drop out visit.
Hematology test, Blood chemistry test, Urinalysis test	Normality - Normal - Abnormal NCS - Abnormal CS
	Shift from baseline to week n, n=6, 14, 26 - Normal or Abnormal NCS - Abnormal CS
	Shift from baseline to final visit - Normal or Abnormal NCS - Abnormal CS

* The laboratory tests will include following test items.

Laboratory Test	Laboratory Test Items(unit)
Hematology test	- WBC ($10^3/\mu\text{L}$) - RBC ($10^6/\mu\text{L}$) - Hemoglobin (g/dL) - Hematocrit (%) - Platelet count ($10^3/\mu\text{L}$) - Neutrophils (%) - Lymphocytes (%) - Monocytes (%) - Eosinophils (%) - Basophils (%)
Blood chemistry test	- BUN (mg/dL) - Creatinine (mg/dL) - Uric acid (mg/dL)

Laboratory Test	Laboratory Test Items(unit)
	
 - Total bilirubin (mg/dL) - Albumin (g/dL) - Total protein (g/dL) - ALT(IU/L) - AST(IU/L) - γ-GTP(IU/L) - Alkaline phosphatase (IU/L) - Glucose (mg/dL) - Total cholesterol (mg/dL)
Urinalysis test	
 - Protein (Albumin) - Glucose - Ketones - WBC - Blood (RBC)

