3.3 Determination of the Sample Size

Total number of subjects: 75 subjects (75 subjects in total with 25 subjects per group considering a dropout rate of 20%)

	Study Group 1	Study Group 2	Control Group	Total Number of Subjects
Number of Subjects	20	20	20	60
Number of Subjects Considering Dropout (20%)	25	25	25	75

This is a Phase 2a exploratory clinical study conducted for the purposes of collecting initial safety and efficacy information on the investigational product GV1001 in patients with progressive supranuclear palsy as well as providing the basis for design, evaluation items, and evaluation methods for subsequent clinical studies. Since this is a study to estimate the clinically significant effect size to demonstrate the efficacy of this investigational product, the number of subjects was not calculated based on statistical considerations. The minimum number of subjects required in a pilot study is 12 subjects²⁾ and approximately 30 subjects can be considered according to the rule of thumb^{3), 4)}. Therefore, by combining these, it is intended to set 20 subjects per group, and a total of 75 subjects with 25 subjects per group will be enrolled considering a dropout rate of 20%.

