5. GENERAL CONSIDERATIONS FOR SUMMARIES AND ANALYSES

5.1 Significance Level

Unless otherwise specified, all statistical tests will be two-sided hypothesis tests performed at the 5% level of significance and all confidence intervals will be two-sided 95% confidence intervals.

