10.3.2 Method of Analysis

Actual values and changes from baseline for continuous clinical laboratory test results will be summarized by treatment group at each time point using descriptive statistics (number of subjects observed, mean, standard deviation, median, minimum, and maximum). In addition, depending on whether the assumption of normality is satisfied, the intragroup comparison will use the paired t-test or Wilcoxon's signed-rank test, while the intergroup comparison (GV1001 0.56 mg/day vs. control group, GV1001 1.12 mg/day vs. control group) will use the two-sample t-test or Wilcoxon's rank-sum test to perform analysis.

For categorical variables, shift tables from baseline visit to each scheduled post-baseline visit, will be generated for clinical laboratory test results using Normal or Abnormal not clinically significant (NCS)/Abnormal clinically significant (CS), by treatment group and overall subjects. The intragroup comparison will use McNemar's test, while the intergroup comparison (GV1001 0.56 mg/day vs. control group, GV1001 1.12 mg/day vs. control group) will use Pearson's chi-square test or Fisher's exact test to perform analysis.

Subjects with normal or abnormal NCS values at baseline that shifted to abnormal CS after baseline on laboratory test will be listed.

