10.3.9. Laboratory Tests

For the laboratory tests of Visit 1 (screening), the results of tests performed within 4 weeks may be used if available, and retesting may be performed only once at the discretion of the investigator. If retesting is performed, the final checking of the inclusion/exclusion criteria will be based on the results of retesting.

Among the blood chemistry test items, HbA1c and coagulation tests, thyroid test, syphilis, acquired immune deficiency syndrome (AIDS) test, and creatinine clearance test will be performed only at Visit 1 (screening). At Visit 1 (screening), the serum FSH tests shall be performed to confirm menopause in women aged ≥ 41 years to < 55 years who have experienced amenorrhea for more than 1 year.

Hematology test	White blood cell (WBC), Red blood cell (RBC), Hemoglobin, Hematocrit, Platelets count, WBC differential count (Neutrophils, Lymphocytes, Monocytes, Eosinophils, Basophils)
Blood chemistry test	Blood urea nitrogen (BUN), Creatinine, Uric acid, Total bilirubin, Albumin, Total Protein, Alanine aminotransferase (ALT), Aspartate aminotransferase (AST), γ -Glutamyl transpeptidase (GTP), Alkaline phosphatase, Glucose, Total Cholesterol, HbA1c (performed only at screening visit)
Serum Follicle Stimulating Hormone test	FSH (Performed only at screening visit for those who require confirmation of menopause)
Urinalysis	Protein (Albumin), Glucose, Ketones, WBC, Blood (RBC)
Blood coagulation test	International normalized ratio (INR) (performed only at screening visit)
Thyroid test	Thyroid stimulating hormone (TSH), free T4 (performed only at screening visit)
Syphilis, AIDS tests	Venereal disease research laboratory (VDRL), or Rapid plasma reagent (RPR), anti-HIV (performed only at screening visit)
Creatinine clearance	This will be confirmed using the Cockcroft-Gault formula. (performed only at screening visit) $CLcr = [(140 - \text{Age (years)}]) \times \text{Weight (kg)} \times 0.85 \text{ (for female subjects)} / 72 \times \text{Serum Creatinine (mg/dl)}$

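### The white-cell differential is analysed only as percentages, so a change in one cell line can show as apparent change in others, and a proportional fall in all lines shows only in total WBC

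*SAP*

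**What the plan says.** The hematology list in SAP 10.3.1 gives the five differential lines in percent ("Neutrophils (%) - Lymphocytes (%) - Monocytes (%) - Eosinophils (%) - Basophils", the last also in percent). Total WBC heads the same list as an absolute count in 10^3/µL. Neither 10.3.1 nor 10.3.2 lists or derives an absolute count for any line.

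The analysis variable for hematology items is the change from baseline at three visits ("Change from baseline at week n = result at week n – result at baseline n=6, 14, 26") and at the final visit. For every continuous item, SAP 10.3.2 states that "Actual values and changes from baseline for continuous clinical laboratory test results will be summarized by treatment group at each time point". It adds within-arm tests, and the comparison of each dose with control "will use the two-sample t-test or Wilcoxon's rank-sum test to perform analysis", according to normality. SAP 5.1 sets the level: "all statistical tests will be two-sided hypothesis tests performed at the 5% level of significance".

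There is also a categorical route. Results are classed as normal, abnormal NCS or abnormal CS, shift tables are produced, and "Subjects with normal or abnormal NCS values at baseline that shifted to abnormal CS after baseline on laboratory test will be listed".

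Protocol 10.3.9 names the item as "WBC differential count (Neutrophils, Lymphocytes, Monocytes, Eosinophils, Basophils") and gives no unit. The percent-only form therefore comes from the SAP.

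**The concern.** A differential percentage is a ratio with total WBC underneath. When one line moves, the denominator moves too, and so do the percentages of lines whose counts are unchanged. The plan nevertheless treats each percentage as a separate continuous outcome with its own p-value.

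Two consequences follow. A change in one line can produce apparent changes in others, and the table does not show which are real. A fall in all lines by the same proportion leaves every percentage where it was. Total WBC then shows that something fell, but not whether one line or several were responsible.

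Laboratory tests are a named safety endpoint (protocol 10.4.4), and evaluating safety is part of the primary objective (SAP 3.1.1). What is at stake is the reading of the by-arm hematology tables. No efficacy analysis is affected.

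**Working it through.** **Inputs from the documents.** Five lines in percent, and WBC in 10^3/µL (SAP 10.3.1). Change from baseline, each dose against control, two-sided 5% (SAP 10.3.1, 10.3.2, 5.1). Group size: 20 evaluable and 25 enrolled per arm (SAP 3.3: "75 subjects in total with 25 subjects per group considering a dropout rate of 20"%). The plan states no figure on this point, so there is none to reproduce.

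**Assumed inputs.** The documents give no blood counts or variances, so all counts and SDs below are illustrative.

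**Formulas.** Percentage of line i = 100 x count_i / WBC. Count of line i = WBC x percentage_i / 100.

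**Step 1: one line falls.** Assume WBC 6.0 and a differential of 60/30/6/3/1%, that is counts of 3.60/1.80/0.36/0.18/0.06. Neutrophils alone fall by 30%, to 2.52, so WBC = 6.0 - 1.08 = 4.92.

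| Line | Count before → after | % before → after | Change in % points |
|---|---|---|---|
| Neutrophils | 3.60 → 2.52 | 60 → 51.22 | -8.78 |
| Lymphocytes | 1.80 → 1.80 | 30 → 36.59 | +6.59 |
| Monocytes | 0.36 → 0.36 | 6 → 7.32 | +1.32 |
| Eosinophils | 0.18 → 0.18 | 3 → 3.66 | +0.66 |
| Basophils | 0.06 → 0.06 | 1 → 1.22 | +0.22 |

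Four rows show a rise although those counts did not change. With a 50% neutrophil fall, WBC is 4.2 and lymphocytes read 1.8/4.2 = 42.86%, a rise of 12.86 points.

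**Step 2: all lines fall in proportion.** With a 25% fall in every line, the counts are 2.70/1.35/0.27/0.135/0.045 and WBC is 4.5. The percentages are still 60/30/6/3/1. WBC shows -1.5; the differential rows show 0.00. This holds only for a proportional fall. Subtracting the same 0.05 from each line moves the percentages by +1.74, +0.43, -0.61, -0.74 and -0.83 points.

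**Step 3: how often the planned tests would reject.** Simulated two-sample t-tests on change from baseline, with assumed mean counts of 3.6/1.8/0.45/0.15/0.03, between-subject log SD 0.25 and lines varying independently. The effect is in one arm only.

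| True change | Per arm, within-subject log SD | Test | Rejects |
|---|---|---|---|
| Neutrophils -30% only | 25, 0.18 | Lymphocyte % | 87% |
| Neutrophils -30% only | 25, 0.18 | Monocyte % | 65% |
| Neutrophils -30% only | 25, 0.18 | Lymphocyte count | about 5% |
| Neutrophils -30% only | 25, 0.18 | Neutrophil % / WBC | about 97% / 95% |
| Neutrophils -30% only | 20, 0.25 | Lymphocyte % | about 50% |
| Neutrophils -10% only | 25, 0.18 | Lymphocyte % | about 15% |
| All lines -25% | 25, 0.18 | Each % | about 5% |
| All lines -25% | 25, 0.18 | WBC | about 100% |
| Lymphocytes -30% only | 25, 0.18 | WBC | 43% |
| Lymphocytes -30% only | 25, 0.18 | Neutrophil % (apparent rise) | 75% |
| Neutrophils -20%, lymphocytes +40% | 25, 0.18 | WBC | 5% |

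A separate run with the 60/30/6/3/1% differential and within-subject log SD 0.20 gives the same pattern. For a 25% neutrophil-only fall, the lymphocyte-percentage test rejects in 52% (20 per arm) and 61% (25 per arm) of trials, against about 5% on counts.

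**Step 4: can a reader recover the counts from the planned tables?** Not from group means. Take one subject with WBC 6.0 and lymphocytes 30%, and another with WBC 4.2 and lymphocytes 42.86%. Each has a lymphocyte count of 1.8. Mean WBC is 5.1 and the mean percentage is 36.43; their product is 5.1 x 0.3643 = 1.86, not 1.8. The counts have to be derived per subject before they are summarised.

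**The case against.** The strongest reply is that total WBC is already analysed as an absolute count, with the same summaries and tests. A reader of the percent-only list might infer that a fall in all lines would go unseen. The documents do not support that: with a 25% proportional fall the planned WBC test rejects in about 100% of simulated trials, and with a 20% fall in 89% to 96% (20 and 25 per arm, log SD 0.20). In the neutrophil-only case, the neutrophil percentage and WBC both flag the real effect in the right direction. This part of the reply stands. It does not answer attribution: WBC does not name the line, it rejects in only 43% of trials for a 30% lymphocyte fall, and at about the nominal 5% when two lines move in opposite directions.

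A reader might also infer that every other line will give a false signal. That is not shown. At 25 per arm with a uniform log SD of 0.18, eosinophil and basophil percentages reject in about 60% and 58% for a 30% neutrophil fall. With assumed CVs of 30% and 40% for these rarer cells the rates drop to about 30% and 19%. Nor do the documents predict cell-line changes of this size. Protocol 3.2 reports anti-inflammatory effects from laboratory and animal experiments and only mild events in humans.

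The documents do not say that the five percentages add to 100, but the distortion needs only a shared denominator. The shift tables, the CS listing and adverse-event reporting are further safety routes. The documents do not say whether CS calls rest on percentages or counts, and those routes do not correct the continuous tests. Finally, the trial is exploratory and no rule depends on a laboratory p-value, so the weight is modest. That stands.

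**Conclusion.** The concern holds in a limited form. As planned, line-level differential results can mislead about which cell line changed, and a proportional fall in all lines is visible only in total WBC, without attribution. The claim that such a fall would be missed altogether does not hold.

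For a 30% neutrophil-only fall, the false lymphocyte-percentage finding occurs in roughly 50% to 87% of simulated trials, against about 5% on counts. Smaller effects give less: about 15% for a 10% fall. All these rates rest on assumed means and variances, independent variation between lines, and percentages taken as shares of total WBC. The direction of the distortion follows from the ratio itself and does not depend on the assumed variances.

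Priority is low. It concerns safety tables in an exploratory trial, the subject-level data needed are already collected, and the primary and secondary efficacy analyses are unaffected.

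**What to change.** In SAP 10.3.1, add absolute neutrophil, lymphocyte, monocyte, eosinophil and basophil counts, derived per subject and visit as WBC x % / 100 in 10^3/µL. Where either component is missing, the count is missing, in line with the no-imputation rule for safety data in SAP 6.1.

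In SAP 10.3.2, apply the change-from-baseline summaries and between-arm tests to these counts. Show the percentages alongside, with a note that they are to be read together with the counts.

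The cost is SAP wording, one derivation per line and five more derived rows in the hematology tables. No new data are needed. The protocol gives no unit for the differential, so the change does not conflict with it.

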10.3.2 Method of Analysis

Actual values and changes from baseline for continuous clinical laboratory test results will be summarized by treatment group at each time point using descriptive statistics (number of subjects observed, mean, standard deviation, median, minimum, and maximum). In addition, depending on whether the assumption of normality is satisfied, the intragroup comparison will use the paired t-test or Wilcoxon's signed-rank test, while the intergroup comparison (GV1001 0.56 mg/day vs. control group, GV1001 1.12 mg/day vs. control group) will use the two-sample t-test or Wilcoxon's rank-sum test to perform analysis.

For categorical variables, shift tables from baseline visit to each scheduled post-baseline visit, will be generated for clinical laboratory test results using Normal or Abnormal not clinically significant (NCS)/Abnormal clinically significant (CS), by treatment group and overall subjects. The intragroup comparison will use McNemar's test, while the intergroup comparison (GV1001 0.56 mg/day vs. control group, GV1001 1.12 mg/day vs. control group) will use Pearson's chi-square test or Fisher's exact test to perform analysis.

Subjects with normal or abnormal NCS values at baseline that shifted to abnormal CS after baseline on laboratory test will be listed.

10.4 Other Safety Analyses

10.4.1 Vital Signs

10.4.1.1 Variable, Definition and/or Derivation

- Systolic blood pressure (mmHg), Diastolic blood pressure (mmHg), Pulse rate (beats/minute), Respiratory rate (breaths/minute), Body temperature (°C), Body weight (kg)
- Change from baseline at week n = Result at week n – Result at baseline, n = 2, 3, 4, 6, 8, 10, 12, 14, 16, 18, 20, 22, 24, 26 (except body weight), n = 6, 14, 26 (body weight)
- Change from baseline at final visit*= Result at final visit* – Result at baseline

* the last visit among regular visit, unscheduled visit and End visit/Drop out visit.

10.4.1.2 Method of Analysis

For vital signs, the measurement values at each visit as well as descriptive statistics (number of subjects observed, mean, standard deviation, median, minimum, and maximum) for the changes from the baseline will be presented by treatment group. In addition, to test the intragroup difference before and after investigational product administration, the paired t-test (if normality assumption is satisfied) or Wilcoxon's signed-rank test (if normality assumption is not satisfied) will be performed depending on whether the assumption of normality is satisfied. To test the difference between the study groups and the control group (GV1001 0.56 mg/day vs. control group, GV1001 1.12 mg/day vs. control group) for the changes from the baseline, the two-sample t-test (if normality assumption is satisfied) or Wilcoxon's rank-sum test (if normality assumption is not satisfied) will be performed depending on whether the assumption of normality is satisfied.

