3.2 Study Design

This is a 24-week, multicenter, randomized, double-blind, placebo-controlled, parallel design, prospective, Phase 2a exploratory clinical study.

If the subject and/or the subject's representative provide a written consent to participate in this clinical study, the required examinations and tests will be performed at the screening visit, and the screening period will run for 4 weeks or shorter.

Subjects who are ultimately determined as eligible by the inclusion/exclusion criteria after screening will be randomized at a 1:1:1 ratio to Study Group 1 (GV1001 0.56 mg/day), Study Group 2 (GV1001 1.12 mg/day), or the placebo group depending on the study site in which they are enrolled. Depending on the randomization results, subjects will be administered the investigational product (study drug or placebo) once weekly for the first 4 weeks (1 month), and then administered 10 times at 2-week intervals for 20 weeks (5 months) for a total of 14 doses over 24 weeks (6 months).

All subjects will visit the study site according to the planned clinical study schedule to receive the investigational product and to be evaluated for efficacy and safety. To ensure the objectivity and accuracy of the study results, the efficacy evaluators evaluating the PSP-rating scale will be limited to neurologists who have been sufficiently educated and trained, and the collection of efficacy and safety evaluation data and biomarkers will be performed in a consistent order at each visit.

※ Neurological drugs administered at a stable dose for at least 1 month prior to a subject's participation in this clinical study (prior to screening) will be continued without changing the dose during the clinical study participation period.

[figure not shown]

Figure. Clinical Study Schematic

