5.6 Baseline Definition

Unless otherwise specified, Baseline is defined as the last observed value without missing prior to the first IP administration.

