11.2.3. Covariate Adjustment

Efficacy endpoints will be analyzed with adjustments for the baseline values as well as for the age and sex.

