11.2.10.3. Vital Signs

For vital signs, the measurement values at each visit as well as descriptive statistics (number of subjects observed, mean, standard deviation, median, minimum, and maximum) for the changes from the baseline will be presented by treatment group. In addition, to test the intragroup difference before and after investigational product administration, the paired *t*-test (if normality assumption is satisfied) or Wilcoxon's signed-rank test (if normality assumption is not satisfied) will be performed depending on whether the assumption of normality is satisfied. To test the difference between the study groups and the control group (GV1001 0.56 mg/day vs. control group, GV1001 1.12 mg/day vs. control group) for the changes from the baseline, the two-sample *t*-test (if normality assumption is satisfied) or Wilcoxon's rank-sum test (if normality assumption is not satisfied) will be performed depending on whether the assumption of normality is satisfied.

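### Continuous laboratory and vital-sign comparisons with control do not use the collected baseline as a covariate, at some cost in precision (minor)

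*SAP*

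**What the plan says.** **Vital signs.** SAP 10.4.1.2 tests each dose against control "for the changes from the baseline, the two-sample t-test (if normality assumption is satisfied) or" the Wilcoxon rank-sum test. The tested variable is explicitly the change from baseline. Protocol 11.2.10.3 has the same pair of tests, and which one is used "will be performed depending on whether the assumption of normality is satisfied".

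**Laboratory values.** In SAP 10.3.2 the comparison of each dose with control "will use the two-sample t-test or Wilcoxon's rank-sum test to perform analysis". The sentence follows a summary of actual values and changes and does not name the tested variable; change is the natural reading. Protocol 11.2.10.2 agrees. This covers the 10 hematology and 12 chemistry items of SAP 10.3.1. Urinalysis and the normal/abnormal classes go to shift tables with chi-square or Fisher tests.

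**Baseline.** SAP 5.6 states: "Baseline is defined as the last observed value without missing prior to the first IP administration". SAP 10.3.1 and 10.4.1.1 define change from that value for each continuous parameter.

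**Covariates.** Protocol 11.2.3 states: "Efficacy endpoints will be analyzed with adjustments for the baseline values as well as for the age and sex". Nothing equivalent is stated for safety, and no reason is given for the difference.

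**The concern.** Subtracting baseline is not the same as adjusting for it. A change score fixes the baseline slope at 1. When the true slope is below 1, the arm that starts higher by chance tends to fall more, with or without a drug effect. The change score is then also noisier than an analysis that estimates the slope.

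Evaluating safety is part of the primary objective (SAP 3.1.1), and the secondary objective uses safety information on both doses to judge further development (SAP 3.1.2). The arms are small. One baseline value also feeds every later visit, so a single chance imbalance in, say, blood pressure can recur across up to 14 post-baseline visits and resemble a sustained effect. SAP 10.3.2 and 10.4.1.2 plan no between-arm difference with a confidence interval, which would help a reader judge this.

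**Working it through.** **Inputs from the documents.** 20 per arm expected to complete and 25 per arm randomized (SAP 3.3); subjects "randomized at a 1:1:1 ratio to Study Group 1" and the two other arms (SAP 3.2); "all statistical tests will be two-sided hypothesis tests performed at the 5% level of significance" (SAP 5.1).

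**Assumptions.** The documents give neither rho nor an SD for any safety parameter. I take rho from 0.3 to 0.9, equal SD at both visits (set to 1), normal data, a linear baseline relation and two arms of n = 20.

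**The plan's own figure.** 20 / (1 − 0.20) = 25 per arm, and 3 × 25 = 75. This reproduces the stated total. The plan gives no figure for the safety comparisons.

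**Precision.**
- Variance of a change score: 2(1 − rho).
- Residual variance under ANCOVA: 1 − rho².
- Ratio, ANCOVA over change score: (1 + rho)/2.
- Cost of estimating the slope: factor 1 + 1/(2n − 4) = 1 + 1/36 = 1.028.

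**Power.** Take the difference that a change-score analysis detects with 80% power by the normal approximation. By the noncentral t that is 77.9% (38 df). The last column gives ANCOVA power for the same difference, with slope cost (37 df).

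**Imbalance.** The expected change-score difference moves by (1 − rho) times the baseline difference, in the opposite direction.

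| rho | (1 + rho)/2 | variance reduction | reduction net of slope cost | shift from a 0.3 SD imbalance | ANCOVA power (change score 77.9%) |
|---|---|---|---|---|---|
| 0.3 | 0.65 | 35% | 33.2% | 0.21 SD | 91.6% |
| 0.5 | 0.75 | 25% | 22.9% | 0.15 SD | 87.4% |
| 0.7 | 0.85 | 15% | 12.6% | 0.09 SD | 83.1% |
| 0.8 | 0.90 | 10% | 7.5% | 0.06 SD | 81.0% |
| 0.9 | 0.95 | 5% | 2.4% | 0.03 SD | 78.8% |

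Example at rho 0.5: 0.75 × 1.028 = 0.771, a net reduction of 22.9%. The net gain vanishes where (1 + rho)/2 × 37/36 = 1, that is at rho = 0.946.

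**How often an imbalance arises.** The SD of a baseline mean difference is √(2/20) = 0.316. About 34% of comparisons exceed 0.3 SD in one direction or the other.

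**Simulation check** (40,000 trials, 20 per arm, no true effect, rho 0.3, 0.5, 0.7 and 0.9). Change-score variance over ANCOVA variance was 1.50, 1.31, 1.15 and 1.03, in line with the formulas. Over all randomizations the change score showed bias of about 0 and type I error of 0.050 to 0.051. Among trials where one arm's baseline mean exceeded the other's by more than 0.3 SD, type I error was 0.102, 0.085, 0.074 and 0.058. The ANCOVA estimate stayed within 0.005 SD of zero in those trials.

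**The case against.** The strongest reply is that nothing here is wrong. The SAP follows the protocol, protocol 11.2.3 confines covariate adjustment to efficacy, and a two-sample test on randomized change scores is valid. That stands. A reader might infer that the safety comparisons are biased, that their error rate is inflated, or that the plan contradicts itself. The documents support none of these: type I error is 5% over randomization, and the raised rates above apply only given an imbalance. Nor is baseline ignored; it is subtracted, so only (1 − rho) of an imbalance remains.

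The second reply is that these p-values carry little weight. This also stands. No success, stopping or dose rule uses them, the sample size has no statistical basis (SAP 3.3), and safety is also judged from adverse-event incidence, shift tables and listings. There are about 334 such tests. Laboratory: 22 items × 4 time points × 2 doses = 176. Vital signs: (5 × 15 + 4) × 2 = 158. A modest gain in each changes the overall safety reading little.

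Third, the size of the gain depends on an assumed rho, and near 0.9 it is close to nil. That is correct, and no single figure should be quoted.

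Two extensions should be resisted. The point does not reach all laboratory results, because urinalysis and the classifications are categorical. The switch between t and Wilcoxon tests according to a normality test comes from the general rule in SAP 5.2 and is a separate matter.

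What remains is that the adjustment uses data already collected, matches the plan's efficacy approach and would supply an interval estimate.

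**Conclusion.** The point holds as a low-severity improvement. The planned tests on continuous hematology, chemistry and vital-sign parameters are valid, but they give up precision and keep (1 − rho) of any chance baseline imbalance. Over rho 0.3 to 0.9 the forgone variance reduction is 35% to 5%, or 33% to 2% net of slope estimation at 20 per arm. It is moderate for poorly correlated parameters and negligible for highly correlated ones. These figures rest on the assumed rho range, equal SDs, normality and linearity. For laboratory values they also rest on reading the tested variable as the change from baseline. The documents do not support calling this an error, a bias or a threat to the trial's conclusions.

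**What to change.** In SAP 10.3.2 and 10.4.1.2, replace the between-arm test for continuous parameters with ANCOVA on the change at each visit, with treatment as factor and that parameter's own baseline as covariate. Report each dose minus control with its 95% CI. This also settles which laboratory variable is tested, because with baseline in the model the treatment estimate is the same for the change and for the follow-up value.

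Fix before unblinding a list of skewed items that will use the log scale or rank ANCOVA. Keep the descriptive tables, and keep the shift tables for urinalysis and other categorical results.

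Record the departure from protocol 11.2.10.2 and 11.2.10.3 in SAP 3.5, which already lists added endpoints and a subgroup analysis that differ from the protocol.

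The cost is SAP wording and a few lines of code, with no new data. The downside is small: a linear baseline term, and a list of transformed items to agree in advance.
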